10.1. Primary Efficacy Endpoint and Analysis

10.1.1. Primary Analysis of the Primary Endpoint

The primary endpoint of this study is the percentage of patients achieving complete corneal healing of PED or corneal ulcer at Week 8, defined as no corneal fluorescein staining in the area of the PED or corneal ulcer as assessed by an independent central reading centre:

- Complete corneal healing: if the question of no corneal fluorescein staining is reported 'Yes' and the greatest diameter of corneal fluorescein staining < 0.5 mm in the area of the PED/ulcer
- No complete corneal healing: if the question of no corneal fluorescein staining is reported 'No' and the greatest diameter of corneal fluorescein staining < 0.5 mm in the area of the PED/ulcer

The primary analysis will be performed on the mITT population. The estimand framework and handling of intercurrent events will be applied as per Section 7.1. Missing data will be imputed with single value imputation as per Section 8.3.2. The CMH test will be used for the analysis, controlling for randomisation strata, i.e. NK stage and region at Week 8.

Confirmatory analysis will be based on the primary estimand. The study will compare 3 different doses of REC 0/0559 with vehicle, resulting in the need of a multiplicity adjustment. Assuming a treatment effect and considering the limited number of patients per group that might impact in the true percentages for the pairwise comparisons, a gate keeping procedure will be applied allocating initially 4% type one error to the 1. REC 0/0559 5.0 μ g/day vs vehicle and 1% type one error to the, 2. REC 0/0559 2.5 μ g/day vs vehicle.

- If the 1. REC 0/0559 5.0 μg/day is significant at 4%, the 2. REC 0/0559 2.5 μg/day will be tested at 5% (1%+4%).
- If the 2. REC 0/0559 2.5 μg/day is significant at 1%, the 1. REC 0/0559 5.0 μg/day will be tested at 5% (4%+1%).

If both the doses are significant vs vehicle then the 3. REC $0/0559~0.5~\mu g/day$ vs vehicle will be tested at 5% level.

In the table output, the number and percentage of patients who achieved corneal healing at Week 8 and the number and percentage of patients who did not will be presented by randomisation strata for each treatment group. In addition, the risk estimates and difference for response (complete corneal healing) with 95% confidence intervals (CIs) to show the effectiveness in each of the treatment groups will be presented by randomisation strata. In case the cell counts of the 2x2 tables are too small, the exact 95% CIs (Clopper Pearson CI) will be reported if available (Clopper & Pearson 1934). The common risk difference, odds ratio (OR), 95% CI, and the CMH test statistics will be presented.

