6.2 Study Endpoints

6.2.1 Primary Efficacy Endpoint

The primary endpoint of this study is the percentage of patients achieving complete corneal healing of PED or corneal ulcer at Week 8, defined as no corneal fluorescein staining in the area of the PED or corneal ulcer as assessed by an independent central reading centre.

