15 STATISTICAL ANALYSIS

A statistical analysis plan (SAP) will be prepared after the protocol is approved. This document will provide further details regarding the definition of analysis variables and analysis methodology to address all study objectives. The SAP will serve as a compliment to the protocol and supersedes it in case of differences.

Subgroup analyses may be defined and added in the SAP, before the database lock, such as gender, NK grade, region or other based on specific characteristics of the enrolled population.

The statistical evaluation will be performed using SAS® software version 9.4 or higher (SAS Institute, Cary, NC). All data will be listed, and summary tables will be provided. Summary statistics will be presented by dose group. For continuous variables, data will be summarised with the number of patients (N), mean, standard deviation, median, minimum, and maximum by treatment group. For categorical variables, data will be tabulated with the number and proportion of patients for each category by treatment group.

No formal interim analysis is planned.

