2.3. Changes from the protocol

The protocol defines the primary endpoint as the capture of complete corneal healing assessed as no corneal fluorescein staining in the area of the prior PED or corneal ulcer by an independent central reading centre. A key secondary endpoint including a more conservative definition assessing the fluorescein staining after 8 weeks of treatment in the area of the initial lesion/ulcer and the persistent staining in the area outside of the lesion/ulcer is also of interest in regards of the post-hoc analysis performed with oxervateTM.

Considering the limited number of patients by group, the hierarchical approach has been replaced by a gatekeeping approach.

An estimand framework that is not outlined in the protocol is added to the SAP to follow current standards for submissions. Due to the implementation of the estimand framework in the SAP, the imputation method for missing data post intercurrent event was adapted to the type of intercurrent events.

The protocol specifies (pooled) site as covariate for the primary and secondary efficacy analyses (CMH test, ANCOVA). As the sites are already pooled within region, which is a randomisation stratum, the variable region at randomisation will be used instead of (pooled) site in the models.

3. Study Objectives

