7.1.3. Second Sensitivity Analysis of the Primary Efficacy Endpoint

The second sensitivity analysis of the primary efficacy endpoint is based on the mITT population but analyses are performed only on observed cases, i.e. no imputations are performed.

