10.1.4. Second Sensitivity Analysis of the Primary Endpoint

As secondary sensitivity analyses, the primary analysis will be repeated for the mITT population with all ICE and true missing data based on observed data only as per Section 7.1.3.

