This document is confidential.

SAP Version: 1.0, 31-May-2024 Controlled Document ID: **3903A.02**, Effective Date 31-Aug-2020

Sponsor: Recordati Rare Diseases; Protocol No.: REC0559-B-001

	REC 0/0559 0.5 µg/day (N=xx)	REC 0/0559 2.5 μg/day (N=xx)	REC 0/0559 5.0 µg/day (N=xx)	Vehicle (N=xx)
Value	x.xx	X.XX	x.xx	
p-value [1]	X.XXX	X.XXX	X.XXX	

n: Number of patients with data available, N: Number of patients within treatment group, PED: Persistent Epithelial Defects, NA: North America, EU: Europe, AE: Adverse Event

Note: Percentage is based on number of patients within treatment group.

Note: Complete corneal healing is defined as no corneal fluorescein staining in the area of the PED or corneal ulcer as assessed by an independent central reading centre.

Note: Occurrence of ICE1, ICE3 and ICE4 are considered as failure at Week 8. Observed data as collected are used for ICE2 and monotone missing values are imputed using last observation carried forward (LOCF) up to Week 8.

- [1]: Vehicle group is used as reference for the risk differences, OR and CMH test. For the confirmatory analysis based on the primary estimand a gate keeping procedure is applied in the following order:
- 1. REC 0/0559 5.0 μ g/day vs vehicle at 0.04 alpha level and if significant, REC 0/0559 2.5 μ g/day vs vehicle at 0.05 alpha level. If both tests are significant, REC 0/0559 0.5 μ g/day vs vehicle is tested at 0.05 alpha level.
- 2. REC 0/0559 2.5 μ g/day vs vehicle at 0.01 alpha level and if significant, REC 0/0559 5.0 μ g/day vs vehicle at 0.05 alpha level. If both tests are significant, REC 0/0559 0.5 μ g/day vs vehicle is tested at 0.05 alpha level.

Analysis dataset: ADxx.SAS7BDAT; Data Source: Listing 16.2.x

Date/time of run: ddmmmyyyy:hh:mm

orogram name>

Programming Note:

See section 15 for Format of output in the SAP.

This document is confidential.

SAP Version: 1.0. 31-May-2024

Controlled Document ID: 3903A.02, Effective Date 31-Aug-2020

Sponsor: Recordati Rare Diseases; Protocol No.: REC0559-B-001

Table 14.2.1.2 Percentage of Patients achieving Complete Corneal Healing of PED or Corneal Ulcer at Week 8 controlling for Disease Stage and Region - Central Reading - Supplementary Estimand (mITT)

	REC 0/0559	REC 0/0559	REC 0/0559	Vehicle
	0.5 μg/day (N=xx)	2.5 μg/day (N=xx)	5.0 µg/day (N=xx)	(N=xx)
Intercurrent events (ICE) up to Week 8, n (%)				
ICE1: Treatment discontinuation due to treatment-related AE	n (xx)	n (xx)	n (xx)	n (xx)

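### SAP 10.1.1 puts the same < 0.5 mm condition on both healed and not healed, so an unhealed eye with 0.5 mm or more of staining fits neither category

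*SAP*

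**What the plan says.** Protocol 6.2.1 has complete healing "defined as no corneal fluorescein staining in the area of the PED or corneal ulcer as assessed by an independent central reading centre". SAP 5.1, SAP 7.1 and the opening sentence of SAP 10.1.1 repeat that definition. The footnote to the primary results shell, Table 14.2.1.1, agrees: "Complete corneal healing is defined as no corneal fluorescein staining in the area of the PED or corneal ulcer". SAP 2.3 describes the protocol endpoint as "complete corneal healing assessed as no corneal fluorescein staining in the area of the prior PED or corneal ulcer", and its list of changes mentions no size condition for the primary endpoint.

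SAP 10.1.1 then turns the definition into two coding bullets. Healed needs a Yes on the no-staining item together with a greatest diameter below 0.5 mm. Not healed applies "if the question of no corneal fluorescein staining is reported 'No' and the greatest diameter of corneal fluorescein staining < 0.5 mm" in the lesion area. The inequality is the same in both; only the Yes or No differs.

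The same section expects a two-way split: patients who healed, and "the number and percentage of patients who did not will be presented by randomisation strata for each treatment group". The below-0.5 mm criterion already has its own place as Other Efficacy Endpoint 1 (SAP 5.4 and 10.4.1).

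**The concern.** Under the endpoint definition, the complement of healed is any staining in the lesion area, whatever its size. The not-healed bullet covers only the part of that complement with a small residual lesion. The plainest failures have no category.

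This is the rule the SAP states for its confirmatory endpoint, and it disagrees with the sentence that introduces it. Nothing in the documents says which text prevails. Protocol section 15 states: "The SAP will serve as a compliment to the protocol and supersedes it in case of differences". The protocol definition therefore does not automatically override the SAP, and the SAP sets no order of precedence between 10.1.1 and its own table footnote. The introduction to SAP section 10 defers algorithms to ADaM documents that are not part of the plan.

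If the rule were programmed as written, the unclassified eyes would be expected more often on vehicle, where more eyes fail to heal. Leaving them out raises the apparent healing rate more on vehicle than on active drug and narrows the risk difference.

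**Working it through.** **Logic check.** Cross the two items the rule uses:

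| No-staining item | Greatest diameter | Endpoint definition | Rule in SAP 10.1.1 |
|---|---|---|---|
| Yes | < 0.5 mm | healed | healed |
| No | < 0.5 mm | not healed | not healed |
| No | ≥ 0.5 mm | not healed | neither |
| Yes | ≥ 0.5 mm (inconsistent reading) | healed on that item | neither |

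The third row is not exotic. The first sample record in the central-reading shell, Listing 16.2.6.1, shows No on both the no-staining item and the < 0.5 mm item.

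**Planning inputs.** SAP 4.3 gives 27% on vehicle and a difference of 45 points, hence 27% + 45 = 72% on active drug. It uses a two-sided alpha of 0.05, about 80% power and 15% dropout. A continuity-corrected comparison of two proportions needs 23 per arm, and 23 × 1.15 = 26.45, rounded up to the plan's 27. (Dividing instead, 23 / 0.85 = 27.06, gives 28.) The sample size is not in dispute; it only supplies the rates.

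**Conditional effect in the observed-case analysis.** SAP 7.1.3 says "analyses are performed only on observed cases, i.e. no imputations are performed", and SAP 10.1.4 says "the primary analysis will be repeated for the mITT population with all ICE and true missing data based on observed data only". An eye with no category would simply be absent. Let p be the true healing rate and f the share of unhealed eyes with 0.5 mm or more, assumed equal in both arms. The fraction omitted is (1 − p)f, and the healing rate among classified eyes is p / [1 − (1 − p)f]. For f = 0.50:

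- vehicle: 0.27 / (1 − 0.73 × 0.50) = 0.27 / 0.635 = 0.425
- active: 0.72 / (1 − 0.28 × 0.50) = 0.72 / 0.860 = 0.837
- difference: 0.412

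| f (assumed) | Vehicle | Active | Difference | Omitted of 27, vehicle | Omitted of 27, active |
|---|---|---|---|---|---|
| 0 | 0.270 | 0.720 | 0.450 | 0 | 0 |
| 0.10 | 0.291 | 0.741 | 0.449 | 2.0 | 0.8 |
| 0.25 | 0.330 | 0.774 | 0.444 | 4.9 | 1.9 |
| 0.50 | 0.425 | 0.837 | 0.412 | 9.9 | 3.8 |
| 0.70 | 0.552 | 0.896 | 0.343 | 13.8 | 5.3 |
| 0.90 | 0.787 | 0.963 | 0.175 | 17.7 | 6.8 |

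These are crude rates, without the stage and region strata. The odds ratio, which SAP 10.1.1 also reports, does not move. Omission multiplies the odds in each arm by 1 / (1 − f), which cancels, leaving (0.72 / 0.28) / (0.27 / 0.73) = 6.95 for every f below 1.

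**Primary estimand.** No figure is given. SAP 10.1.1 calls for single-value imputation of missing data. SAP 8.3.2 says the same for analyses under the primary estimand framework, but also says that data missing without an intercurrent event are multiply imputed under missing at random. How an uncategorised eye would be handled there cannot be determined from the text.

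**The case against.** The best counter-argument is a different reading. The central grading form holds two Yes/No items, one for no staining and one for < 0.5 mm, and the sample rows in Listing 16.2.6.1 show only Yes/Yes and No/No. If the second bullet is shorthand for No on both, an eye with 0.5 mm or more is classified after all. That reading needs words the bullet does not contain. It also leaves an eye with some staining below 0.5 mm without a category, although the definition makes that eye a failure too. The rule is not exhaustive either way, and the table above would then apply with f redefined as the share of unhealed eyes below 0.5 mm.

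It is also fair to say that the intent is plain from the rest of the SAP. A programmer may well code the complement, in which case no result changes, and the quality control in SAP section 16 should expose a rule that leaves most vehicle failures uncategorised. This limits the likely harm but does not make the stated rule correct.

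Three narrower points stand:

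- The omitted counts use all 27 per arm. With 15% dropout, 27 × 0.85 = 22.95 remain, and at f = 0.90 the vehicle count is 22.95 × 0.657 = 15.1 rather than 17.7. The rates are unaffected.
- The Table 14.2.1.4 footnotes base percentages on the number of patients in the treatment group. The printed healed percentages need not shift; the effect falls on a risk difference computed among classified eyes.
- In the healed bullet the < 0.5 mm condition is redundant for an eye without staining, rather than contradictory.

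**Conclusion.** The concern holds. As written, the coding rule for the confirmatory endpoint is not exhaustive and conflicts with the definition used everywhere else in the protocol and SAP. That conclusion rests on the text alone and is the reason the rule must be corrected.

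The numerical consequence is secondary and conditional. It requires literal programming, and it is quantified only for the observed-case sensitivity analysis at an assumed share f equal in both arms. The change is negligible at shares of 10% to 25% (under one point) and large only at high shares, falling to 17.5 points at 90%. No effect is claimed on the confirmatory test, the power or the sample size.

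**What to change.** Before unmasking, delete the < 0.5 mm condition from the not-healed bullet of SAP 10.1.1, so that a No on the no-staining item for the lesion area means not healed at any diameter. Delete it from the healed bullet as well, so that a Yes means healed. This deals with both readings of the rule and restores the definition in Protocol 6.2.1 and SAP 5.1. Put the same wording in the ADaM specification. Keep the < 0.5 mm threshold for Other Efficacy Endpoint 1. Optionally, query with the reading centre any record that has a Yes on no staining and a diameter of 0.5 mm or more.

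The cost is one or two lines of SAP text and the matching specification line, made before database lock. No new data are needed and the endpoint itself does not change.

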10.1.2. Supplementary Estimand of the Primary Endpoint

The supplementary estimand of the primary endpoint will be performed according to the estimand framework and definitions of intercurrent events in Section 7.1.1. Missing data will be imputed with MI as per Section 8.3.2.

The same table output will be created as for the primary analysis.

10.1.3. First Sensitivity Analysis of the Primary Endpoint

As first sensitivity analyses, the primary analysis will be performed according to the estimand framework and definitions of intercurrent events in Section 7.1.2. Missing data will be imputed with MI as per Section 8.3.2.

10.1.4. Second Sensitivity Analysis of the Primary Endpoint

As secondary sensitivity analyses, the primary analysis will be repeated for the mITT population with all ICE and true missing data based on observed data only as per Section 7.1.3.

10.1.5. Supportive Sensitivity Analysis of the Primary Endpoint

As supportive sensitivity analyses, the primary analysis will be repeated for the PP population according to the estimand framework and definitions of intercurrent events in Section 7.1.4.

10.2. Key Secondary Efficacy Endpoint and Analyses

The key secondary endpoint of this study is the percentage of patients achieving complete corneal healing of PED or corneal ulcer at Week 8, defined as no corneal fluorescein staining in the area of the PED or corneal ulcer and no persistent staining outside of corneal lesion elsewhere in the cornea (i.e. not changing in shape and/or location at different timepoints) as assessed by an independent central reading centre:

The analysis will be performed on the mITT population according to the primary estimand framework and ICE definitions of the primary efficacy endpoint (Section 7.2) using the CMH test controlling for randomisation strata at Week 8. Missing data will be imputed with single value imputation as per Section 8.3.2. A similar table output as for the primary efficacy analysis will be provided..

10.3. Secondary Efficacy Endpoints and Analyses

If significance is reached for the three doses on the primary endpoint, the gate keeping procedure used for the primary endpoint will also be used for secondary endpoints (in the hierarchical order as listed in section 5).

10.3.1. Secondary Efficacy Endpoint 1

The percentage of patients who achieve a \geq 5-, 10-, and 15-letter mean improvement in BCDVA by the ETDRS chart at Week 8 compared to baseline will be summarised for all patients and for patients with a central location of the PED or corneal ulcer.

The analysis will be performed on the mITT population according to the estimand framework and ICE definitions of the binary secondary efficacy endpoints (Section 7.2) using the CMH test controlling for randomisation strata at Week 8. Missing data will be imputed with single value imputation as per Section 8.3.2. A similar table output as for the primary efficacy analysis will be provided by all patients and by only patients with a central location of PED or corneal ulcer.

A descriptive frequency table will present the number and percentage of patients per visit and overall that have reported finger counting, hand motion, light perception or no light perception based on observed data.

10.3.2. Secondary Efficacy Endpoint 2

The percentage of patients achieving complete corneal healing of PED or corneal ulcer at Week 8, defined as no corneal fluorescein staining in the area of the PED or corneal ulcer as assessed by the investigator, will be summarised. The analysis will be performed on the mITT population according to the estimand framework and ICE definitions of the binary secondary efficacy endpoint (Section 7.2) using the CMH test controlling for randomisation strata at Week 8. Missing data will be imputed with single value imputation as per Section 8.3.2. The same table output as for the primary efficacy analysis will be created.

10.3.3. Secondary Efficacy Endpoint 3

The time to complete corneal healing of PED or corneal ulcer is defined as the time from treatment start to no corneal fluorescein staining in the area of the PED or corneal ulcer as assessed by an independent central reader in days. Treatment group and randomisation strata, disease stage and region, are used as covariates. Patients who do not achieve complete corneal healing until end of treatment (V8/D56) are censored at date of V8/D56 or last available assessment date if early terminated in case no intercurrent event (ICE) occurred. The censoring date after the occurrence of an ICE and respective imputation will be the actual assessment date at (V8/D56), if available. In case the patient has no efficacy assessment done at (V8/D56), the censoring time (days) after the ICE occurrence will be set to Day 56 which is the last scheduled efficacy assessment day in the 8 week treatment administration period as planned per protocol. The analysis will be performed on the mITT population according to the estimand framework and ICE definitions for the time to event endpoints (Section 7.2). Missing data will be imputed with single value imputation as per Section 8.3.2.

The hazard ratios (HRs) and their 95% Wald CIs and p-values, as well as the estimate and 95% CI for the median, 25% and 75% quartiles of time to complete corneal healing, will be reported in a table; the survival probability for the treatment groups will be plotted in a figure.

10.3.4. Secondary Efficacy Endpoint 4

The time to complete corneal healing of PED or corneal ulcer is defined as the time from treatment start to no corneal fluorescein staining in the area of the PED or corneal ulcer as assessed by the investigator in days. Treatment group and randomisation strata, disease stage and region are used as covariates. Patients who do not achieve complete corneal healing until end of treatment (V8/D56) are censored at date of V8/D56 or last available date if early terminated terminated in case no intercurrent event (ICE) occurred. The censoring date after the occurrence of an ICE and respective imputation will be the actual assessment

date at (V8/D56) if available. In case the patient has no efficacy assessment done at (V8/D56), the censoring time (days) after the ICE occurrence will be set to Day 56 which is the last scheduled efficacy assessment day in the 8 week treatment administration period as planned per protocol. The analysis will be performed on the mITT population according to the estimand framework and ICE definitions for the time to event endpoints (Section 7.2). Missing data will be imputed with single value imputation as per Section 8.3.2..

The HRs and their 95% Wald CIs and p-values, as well as the estimate and 95% CI for the median, 25% and 75% quartiles of time to complete corneal healing, will be reported in a table; the survival probability for the treatment groups will be plotted in a figure.

10.3.5. Secondary Efficacy Endpoint 5

Deterioration of the disease at Week 8 is defined as an increase in lesion size ≥ 1 mm compared to baseline as assessed by the investigator, or mean decrease in BCDVA by > 5 letters compared to baseline, or progression in lesion depth to corneal melting or perforation, or onset of infection.

The analysis will be performed on the mITT population according to the estimand framework ind ICE definitions of the binary secondary efficacy endpoint (Section 7.2) using the CMH test controlling for randomisation strata at Week 8. Missing data will be imputed with single imputation as per Section 8.3.2. The same table output as for the primary efficacy analysis will be created.

10.3.6. Secondary Efficacy Endpoint 6

An ANCOVA will be performed for the mean change in BCDVA from baseline to Week 8 in all patients and in patients with a central location of the PED or corneal ulcer with missing values imputed as per estimand strategies and definitions of intercurrent events for continuous secondary efficacy endpoints as described in Section 7.2. Missing data will be imputed with MI as per Section 8.3.2. The least squares mean (LSM) estimates and 95% CIs of each treatment group as well as the LSM differences, 95% CIs, and p-values from the comparison between the REC 0/0559 groups and vehicle group will be reported separately for all patients and for patients with a central location of PED or corneal ulcer. Descriptive summary of the mean change from baseline at Week 8 based on imputed data will also be presented. In addition, BCDVA values and changes from baseline are summarised descriptively by visit based on observed data only.

10.3.7. Secondary Efficacy Endpoint 7

The percentage of patients at Week 8 with improvement in corneal sensitivity from baseline, as measured by the Cochet-Bonnet aesthesiometer, will be summarised.

The corneal sensitivity is assessed as the mean (cm) of the results of the assessment of the 5 cornea sections (central, superior-nasal, inferior-nasal, superior-temporal, inferior-temporal). The mean is calculated based on all available results at a certain visit. Assessments of cornea locations that are not applicable are disregarded and not included in the calculation of the mean.

The analysis will be performed on the mITT population according to the estimand framework and ICE definitions of the binary secondary efficacy endpoints (Section 7.2) using the CMH test controlling for randomisation strata at Week 8. Missing data will be imputed with single value imputation as per Section 8.3.2. Imputation is performed on the responder/non-responder variable, derived from the mean values calculated from the 5 cornea sections at the respective visits. The same table output will be created as for the primary efficacy analysis.

